## 4.3 Subgroups

The following subgroups may be used to provide further information on the primary efficacy endpoint and other clinical and virologic endpoints:

- Use of positive pressure ventilation
- Use of endotracheal intubation
- Time from onset of symptoms to VIS410 therapy
- Number of oseltamivir doses prior to VIS410
- Age categorization (<65 years, ≥65 years)
- Presence of underlying chronic lung disease
- Presence of coincident pneumonitis (pneumonia) at baseline
- Influenza A subtype
- Enrollment geographic region: Tiered assessments: initially, dichotomous (Northern Hemisphere and Southern Hemisphere), then with each hemisphere broken into two groups: North America (Canada and US) and Europe (Belarus, Belgium, Bulgaria, Estonia, France, Georgia, Latvia, Russia, Serbia, Spain, Ukraine and Georgia); and Asia/Oceania (Australia, Malaysia, New Zealand, Singapore, and Thailand) and South Africa. Enrollment geographic region: (northern hemisphere vs southern hemisphere)
- MITT subset comprised of subjects with positive baseline viral cultures based on TCID50
- Baseline HAI titer category (to matched virus subtype) (≤40 or >40)
- Time between onset of symptoms of influenza and treatment (< 72 hours or ≥ 72 hours)

January 17, 2019

## **5 STUDY SUBJECTS**

### **5.1 Analysis Populations**

#### **5.1.1 All Enrolled Subjects**

All enrolled subjects will include all subjects with a non-missing informed consent date. All enrolled subjects will be used for subject data listings and disposition summaries.

#### **5.1.2 Intent-to-Treat Population**

The intent-to-treat (ITT) population will include all subjects randomized to treatment. Any ITT population summaries will be based on the treatment to which they were randomly assigned.

#### **5.1.3 Modified Intent-to-Treat Population**

The modified ITT (MITT) population will include all subjects who receive IV study drug and are confirmed influenza A positive. The MITT population summaries will be based on the treatment to which they were randomly assigned. All efficacy analyses including the primary efficacy analyses are performed in the MITT population.

#### **5.1.4 Safety Population**

The safety population will include all ITT subjects who received IV study drug. The safety population summaries will be based on the actual treatment received.

#### **5.1.5 Pharmacokinetic Population**

The PK population will include all subjects who receive IV study drug and have at least 1 PK parameter that can be calculated.

### **5.2 Protocol Deviations**

Major protocol deviations are compliance issues that have an impact on subject safety or the scientific integrity of the study data. All deviations will be evaluated and classified as major or minor by the study team before database lock and unblinding. Major and minor deviations will be summarized by treatment group with counts and percentages of subjects with at least 1 deviation. If a subject has both minor and major deviations, that subject will be counted as having a major deviation. All deviations will be listed.

### **5.3 Disposition of Subjects**

The following subject data will be summarized for each treatment group and overall:

- Number and percentage of subjects in each analysis population
- Number and percentage of subjects who completed the study
- Number and percentage of subjects who prematurely discontinued the study as well as number and percentage of subjects for each reason for discontinuation.

Percentages will be calculated using the ITT population as a denominator. All disposition data will be listed.

An additional disposition summary will be presented for the MITT population along with a summary of enrollment by region and site for each treatment group and overall. Region will be

January 17, 2019

categorized as North America (Canada and US), South Africa, Asia and Oceania (Australia, Malaysia, New Zealand, Singapore, and Thailand), and Europe (Belarus, Belgium, Bulgaria, Estonia, France, Georgia, Latvia, Russia, Serbia, Spain, Ukraine and Georgia)).

A listing of subject enrollment and disposition information will be provided for all subjects. An additional listing of subjects who prematurely discontinued the study will also be presented. Inclusion of subjects into each of the analysis populations (ITT, Safety, MITT, and PK) will also be listed.

## 6 DEMOGRAPHICS AND BASELINE CHARACTERISTICS

### 6.1 Demographics and Baseline characteristics

Descriptive statistics of the general demographic and Baseline characteristics for each treatment group and overall will be presented. Baseline variables age (years), height (cm), weight (kg), body mass index (BMI,  $\text{kg}/\text{m}^2$ ), and time since onset of influenza symptoms will be summarized with n, mean, SD, median, minimum and maximum; time to onset of influenza will also be categorized (<24 hours, 24 to < 48 hours, 48 to <72 hours, 72 to <96 hours, or  $\geq 96$  hours) and summarized with counts and percentages. Individual baseline HAI antibody status will be to the infecting virus subtype for each individual, and will be dichotomized (antibody titer  $\leq 1:40$ , antibody titer  $> 1:40$ ). Counts and percentages will be presented for each category of gender, race, ethnicity, positive pressure ventilation status, smoking status, vaccination status, confirmed influenza A by method of diagnosis (RAT, PCR, TCID50, FIA, ELISA), HAI titer and influenza subtype. Counts and percentages will also be presented for comorbidities defined based on specific MedDRA terms and BMI (see Addendum 1) and number of days of Oseltamivir use prior to Study Day 1.

The demographic and Baseline data will be summarized for the ITT and MITT populations. All demography and Baseline data will be listed.

The following definitions and conversions will be used:

- Height (in) \*2.54 = height (cm)
- Weight (lb) /2.2 = weight (kg)
- BMI ( $\text{kg}/\text{m}^2$ ) = weight (kg)/ height ( $\text{m}^2$ )
- Time since onset of influenza (hours) = date/time of infusion start – date/time of onset of symptoms. If onset time is missing, it will be imputed as 00:00 on the 24-hour clock.

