#### 3.2 Secondary Endpoints

- Among subjects requiring supplemental oxygen therapy at the time of enrollment with baseline room air oxygen saturation of  $\leq 92\%$ , time to cessation of oxygen (O2) support resulting in stable oxygen saturation (SpO2) by pulse oximetry. Stable SpO2 is defined as two consecutive SpO2 values of  $> 92\%$  on room air that are at least 8 hours apart.
- For any subject requiring supplemental oxygen therapy at the time of enrollment (regardless of oxygen saturation), time to cessation of oxygen support.
- The difference between VIS410 + oseltamivir and oseltamivir alone treatment groups in the following endpoints:
  - Assess viral load parameters in respiratory samples (MITT population, and subsets), specifically:
    - Peak virus concentration by qRT-PCR
    - Viral nasopharyngeal qRT-PCR AUC, BL to Day 5 and BL to Day 7
      - Include baseline-adjusted and non-adjusted comparisons.
    - Viral shedding by qRT-PCR versus time
      - Include baseline-adjusted and non-adjusted comparison.
    - Percentage of subjects in whom peak qRT-PCR value occurred post-baseline
    - Viral nasopharyngeal qRT-PCR AUC, BL to Day 7 and BL to Day 14
    - Peak virus concentration by TCID50

January 17, 2019

- Percentage of subjects in whom peak TCID50 value occurred post-baseline Viral nasopharyngeal TCID50 AUC, BL to Day 5 and BL to Day 7
  - For TCID50 AUC analyses, perform in both the MITT population and the MITT population subset comprised of subjects with positive BL nasopharyngeal viral cultures
  - Include baseline-adjusted and non-adjusted comparisons.
- Viral shedding by TCID50 versus time
  - Include baseline-adjusted and non-adjusted comparison.
- Percentage of subjects with negative viral cultures by nominal study day (Day 3, Day 5, Day 7)
  - Perform this analysis in both the MITT population, and the MITT population subset comprised of subjects with positive BL nasopharyngeal viral cultures
- Kaplan Meier analysis of time to negativization of viral cultures, by treatment arm
  - Perform this analysis in both the MITT population, and the MITT population subset comprised of subjects with positive BL nasopharyngeal viral cultures
- Additional subset analyses will examine the above outcomes by:
  - Virus strain family, H1N1 versus H3N2
  - Duration of symptoms prior to treatment (< 72 hours, ≥ 72 hours)

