### 9.2.2 Time to Cessation of O2 Support

Among subjects requiring supplemental oxygen therapy at the time of enrollment with baseline room air oxygen saturation of  $\leq 92\%$ , time to cessation of O2 support will be analyzed using a Cox proportional hazards model where cessation of O2 support is defined as the finding of stable SpO2 at two consecutive room air SpO2 values that are separated by at least 8 hours greater than 92%. In the event that a subject has only one room air SpO2 measurement but has been stable off oxygen (for instance as an outpatient), the second value may be a carry forward of the prior measurement. Time from onset of symptoms to VIS410 treatment and the number of doses of oseltamivir (Tamiflu) prior to VIS410 treatment for the current case of influenza will be included as covariates in the analysis. P-values (using the Wald statistic) for each VIS410 dose versus placebo, VIS410 total versus placebo and VIS410 4000 mg versus 2000 mg will be presented.

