#### **9.2.5 Healthcare resource utilization**

Descriptive statistics will be used to compare the total number of days in the hospital and/or ICU from admission to discharge, number of subjects requiring ICU admission post-randomization, overall number of days in the ICU, number of hours on ventilation, rehospitalization due to influenza A relapse/reinfection, the total number of days of oseltamivir therapy, and the total number of days to resumption of usual activities by treatment group.

Time (number of days) to resumption of usual activities will be determined from the VAS (scale ranged from 0 to 10, where 0 indicates subject is unable to perform any of his/her usual activities prior to influenza onset, and 10 indicates subject is able to fully perform all usual activities). Time to resumption of usual activities will be calculated as the difference between the first day the subject reports a score of 10 and Day 1. If a subject does not report a score of 10 by Day 14, a value of 14 will be used in the analysis. This evaluation will be performed using the MITT population. Additional analyses of VAS scores will reflect summaries of mean VAS scores by study day (up to Day 14), along with change from baseline and percent change from baseline will be generated; p-values will be based on ANOVA using rank transformation of VAS scores. VAS summaries will also be generated in the subsets of subjects with time from onset of symptoms to treatment < 72 hours or ≥ 72 hours. Mean VAS scores by study day along with standard deviations will be presented in figures, overall subjects and in the indicated subsets.

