### 9.2.10 Time to Resolution of Viral Load

Two analyses of median time to resolution of viral load, as determined by qRT-PCR or TCID50 results, and the 95% CI about the median, will be presented using Kaplan-Meier methods. Additional exploratory statistical analyses will be conducted to determine the differences in Kaplan-Meier curves using a log-rank test. Time to resolution of viral load will be assessed on all samples in the MITT population collected through the Day 7 visit for TCID50 analysis and

January 17, 2019

through the Day 14 visit for qRT-PCR analysis. For missing data on Day 1 post-dose, Day 3, Day 5, and Day 7, the analysis will be conducted without imputation and with the last observable measurement carried forward (LOCF). For missing data on Day 1 predose, the analysis will be conducted by replacing the missing data with the Day 1 post-dose observable measurement. Subjects missing both Day 1 predose and Day 1 post-dose virology data will be removed from the analysis. Resolution of viral load is considered to be one BLQ or lower measurement with no samples following that which are greater than the BLQ.

The following virology parameters will be derived:

- Time to resolution of viral load from end of infusion
  - Number of days from end of infusion until virus is no longer detectable (at or below the limit of detection) with no samples following that are greater than the BLQ through the Day 7 (TCID50) or Day 14 (PCR) visit
  - If virus is still above level of detection at Day 7 (TCID50) or Day 14 (PCR) visit, the value will be censored the on Day 7 visit for TCID50 or Day 14 (PCR)
- Time to resolution of viral load from onset of symptoms
  - Number of days from onset of symptoms until virus is no longer detectable (at or below the limit of detection) with no samples following that are greater than the BLQ through the Day 7 (TCID50) or Day 14 (PCR) visit
  - If virus is still above level of detection at Day 7 (TCID50) or Day 14 (PCR) visit, the value will be censored the on Day 7 visit for TCID50 or Day 14 (PCR)

The above analysis will also be performed for the MITT subset comprised of subjects with a positive baseline viral culture based on TCID50.

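### For subjects with no recorded symptom-onset time, imputing 00:00 lengthens time since onset by up to 24 hours and can only move subjects from the under-72-hour subset to the 72-hours-or-more subset

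*SAP*

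**What the plan says.** The definition in SAP 6.1 is "Time since onset of influenza (hours) = date/time of infusion start – date/time of onset of symptoms". The next sentence gives the rule for a missing clock time: "If onset time is missing, it will be imputed as 00:00 on the 24-hour clock".

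Time from onset to treatment is then used in several places:

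- SAP 6.1 tabulates it in 24-hour bands as a baseline characteristic.
- SAP 4.3 lists the subgroup "Time between onset of symptoms of influenza and treatment (< 72 hours or ≥ 72 hours".
- SAP 3.2 has the virology subset "Duration of symptoms prior to treatment (< 72 hours, ≥ 72 hours", repeated in 9.2.8.
- SAP 9.2.5 summarises VAS scores in the "subsets of subjects with time from onset of symptoms to treatment < 72 hours or ≥ 72 hours". The SAP change table shows that this was added in version 2.0 at the sponsor's request.
- SAP 9.2.2 enters "Time from onset of symptoms to VIS410 treatment and the number of doses of oseltamivir" as Cox covariates for time to cessation of oxygen support.
- SAP 9.2.10 uses onset as a time origin: "Number of days from onset of symptoms until virus is no longer detectable".

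None of these sections gives another derivation, so the natural reading is that the 6.1 rule applies to all of them. The SAP does not say so. It plans no sensitivity analysis for this imputation, and neither document says how many onset times are missing.

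**The concern.** A fixed clock time at one end of the possible range gives an error that always has the same sign. Subjects with a recorded time keep their true value, while subjects without one get a value that is never too short. One variable then mixes two scales. Near a cut-off, a one-sided error moves subjects in one direction only: the under-72-hour subset loses members and the other subset gains subjects who were in fact treated earlier.

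Missing times are plausible. Onset is obtained by interview at screening, up to 5 days after the event, from hospitalised patients who may have been consented through a representative. SAP 2.2 says the study is meant to identify endpoints for Phase 3, so a contrast between early and late treatment could be read with interest.

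**Working it through.** The plan states no figure on this point, so there is none to reproduce.

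**Notation.** Let D be the calendar days from onset date to infusion date, t the infusion clock time and u the true onset clock time (hours).

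- True time = 24D + t − u
- Derived time under the 00:00 rule = 24D + t
- Error = u, which runs from 0 to just under 24 h and is never negative

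Example: onset at 20:00, infusion at 14:00 three days later. True time = 72 + 14 − 20 = 66 h; derived time = 72 + 14 = 86 h.

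**Mean error under assumed onset times.** Evenly over 24 h: 12 h. Over 07:00–23:00: 15 h. Over 05:00–11:00: 8 h. Over 17:00–23:00: 20 h.

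**Who can cross 72 h.**

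- D ≤ 2: derived time is at most 48 + t, below 72. No crossing.
- D ≥ 4: true time is at least 96 + t − u, above 72. No crossing.
- D = 3: derived time is 72 + t, so every such subject is placed in ≥72 h. The true value is below 72 h exactly when u > t.

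Nobody moves downward. Among missing-time subjects with D = 3, the share truly below 72 h is 50% if u and t are both uniform over 24 h, and 39.5% if infusions fall between 09:00 and 20:00. Across the onset patterns tried it ranges from 3% to 93%.

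**Expected number moved.** Assume true time uniform over 0–120 h (the 5-day entry window) and u uniform over 24 h. The share of missing-time subjects moved is mean(u)/120 = 12/120 = 10%, or 10/60 = 16.7% of those truly below 72 h. Among 120 subjects with missing rate m, the expected number is 120 × m × 0.10.

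| Missing rate | Subjects moved |
|---|---|
| 5% | 0.6 |
| 10% | 1.2 |
| 25% | 3.0 |
| 50% | 6.0 |

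**What noon would change.** Assume infusions between 10:00 and 20:00 (mean 15:00) and elapsed time over 0–120 h, so that one missing-time subject in five has D = 3.

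- 00:00 rule, onset uniform over 24 h: moved up = 0.2 × (24 − 15)/24 = 7.5%; moved down = 0.
- 00:00 rule, onset 06:00–24:00: moved up = 0.2 × (24 − 15)/18 = 10.0%; moved down = 0.
- Noon rule: derived time on D = 3 is 60 + t, so the subject is placed in ≥72 h whenever infusion is at 12:00 or later. Integrating over t gives the figures below.

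Mean error and root mean square error (RMSE) come from simulation under the same assumptions, using the midpoint rule for same-day onset.

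| Missing-time subjects | 00:00, onset 0–24 h | Noon, onset 0–24 h | 00:00, onset 06–24 h | Noon, onset 06–24 h |
|---|---|---|---|---|
| Mean error (h) | 12.0 | 0.5 | 15.0 | 3.4 |
| RMSE (h) | 13.9 | 6.7 | 15.9 | 6.1 |
| Moved up at 72 h | 7.5% | 5.3% | 10.0% | 7.1% |
| Moved down at 72 h | 0% | 1.8% | 0% | 1.1% |
| Total misclassified | 7.5% | 7.2% | 10.0% | 8.2% |

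Noon removes most of the mean error and at least halves the RMSE. It hardly reduces misclassification at 72 h, and what remains still runs mostly upward.

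**The case against.** The strongest reply is that the deciding input is absent. Without a missing rate the effect could be under one subject in 120, and a dedicated onset interview makes a low rate possible. That stands, and it is why the size is given only as a range.

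Second, the reach of the 6.1 rule is partly inferred. Section 9.2.10 counts days from onset; if those days come from dates, the clock time does not matter there. That also stands.

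Third, any fixed clock time is a convention, SAP 4.2 uses similar earliest-date rules for some partial dates, and noon barely improves classification at 72 h. This is right about the cut-off but not about the hours variable, where the gain in mean error and RMSE is clear and nearly free. SAP 9.2.8 and 9.2.10 already analyse missing post-baseline virology values both with and without imputation; onset time gets one extreme value and no check.

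Three stronger readings are tempting, and the documents do not support them:

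- **That time since onset is overstated by about 12 hours in general, or that subjects treated within 72 hours move as a group.** Recorded times are unaffected, 12 hours is a mean under one assumption, and only the D = 3 subjects with u > t cross.
- **That the treatment comparison is biased.** The rule is prespecified, identical in every arm and uses no outcome data, and the Day 7 model in SAP 9.1 does not name this variable.
- **That eligible subjects would appear to breach the 5-day entry limit, with consequences.** No planned analysis uses the derived variable for eligibility, deviations or membership of the MITT population.

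**Conclusion.** The concern holds in a limited form and is minor. The direction is certain, because it is arithmetic: for missing-time subjects the error is 0 to just under 24 h, always upward, and any crossing of 72 h goes from the earlier to the later subset.

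The size is conditional. About 1 of 120 subjects at 10% missing and 3 at 25% rests on onset and elapsed time being evenly spread and on a missing rate that the documents do not state.

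What is distorted is the 24-hour baseline bands, the 72-hour VAS and virology subsets, the Cox covariate for oxygen cessation and, if computed from clock times, viral resolution from onset. The 4.3 subgroups are optional, and the SAP presents p-values as informative only, which limits the stakes further.

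**What to change.** In SAP 6.1, impute a missing onset time as 12:00 on the onset date, or as the midpoint between 00:00 and infusion start when onset is on the infusion date. State that the same derived variable serves the 72-hour subsets and the Cox covariate, and say whether 9.2.10 counts from dates or from clock times.

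Flag imputed times and report their number by arm.

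Repeat the 72-hour subset results in one of two ways. Calendar days from onset put all subjects on the same scale. Alternatively, exclude imputed-time subjects infused on the third calendar day after onset; under either imputation rule these are the only ones whose subset is in doubt.

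The cost is a few lines of SAP text, one derivation, one flag and a repeat of existing tables. Some misclassification will remain, because the true clock time is unknown. If few times are missing, the count alone will show that the point does not matter.

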### 6.2 Medical history

Medical history will be coded using the Medical Dictionary for Regulatory Activities (MedDRA) Version 20.1 and summarized by System Organ Class (SOC), Preferred Term (PT), and treatment with counts and percentages in the ITT and MITT populations. A subject will only be counted once in an SOC and an SOC/PT combination.

All medical history data will be listed.

January 17, 2019

### **6.3 Prior medications**

Prior medications are defined as medications that start before the study drug IV infusion. Prior medications will be coded with the World Health Organization Drug (WHODrug) Dictionary, Sep 2017 and summarized by Anatomical Therapeutic Chemical (ATC) Level 4, PT, and treatment in the ITT and MITT populations. A subject will only be counted once in an ATC class and an ATC class/PT combination. All eCRF medication data will be listed, including the WHO Drug ATC class, PT and the investigators verbatim description of the medication.

## **7 CONCOMITANT MEDICATIONS**

Concomitant medications are defined medications that are being taken while on study drug. Any prior medication that cannot be confirmed as stopping before the start of study drug IV infusion will be classified as both a prior and a concomitant medication. Concomitant medications will be coded with the WHODrug, Sep 2017 dictionary, and summarized by ATC Level 4, PT, and treatment in the safety population. A subject will only be counted once in an ATC class and an ATC class/PT combination. Medications that are ongoing on the date of study drug IV infusion will be summarized as both prior and concomitant. All eCRF medication data will be listed, including the WHO Drug ATC class, PT term, the investigators verbatim description and classification as prior, concomitant or both. Medications will be sorted by medication start date within subject.

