EC	ethics committee
EC ₅₀	half-maximal effective concentration
ECG	electrocardiogram
EDC	electronic data capture (system)
ELISA	enzyme-linked immunosorbent assay
ESRD	end-stage renal disease
ET	end of therapy
FDA	Food and Drug Administration
FIA	fluorescent immunoassay
FluPRO Questionnaire	Influenza Patient Reported Outcomes (FluPRO) Questionnaire
GCP	Good Clinical Practice
GI	gastrointestinal
GLP	Good Laboratory Practice
HAI	hemagglutination inhibition assay
IC ₅₀	half-maximal inhibitory concentration
ICF	Informed Consent Form
ICH	International Conference on Harmonisation
ICU	intensive care unit
IEC	independent ethics committee
IgG1	immunoglobulin G1

Abbreviation	Definition
IRB	institutional review board
ITT	intent-to-treat
IV	intravenous
IWRS	Interactive Web Response System
LFU	last follow-up
LSLV	last subject last visit
MedDRA	Medical Dictionary for Regulatory Activities
MITT	modified intent-to-treat
NOAEL	no-observed–adverse-effect level
NONMEM	software used for population pharmacokinetic modeling
NSAID	nonsteroidal anti-inflammatory drug
O ₂	oxygen
PCR	polymerase chain reaction
PK	pharmacokinetic
PO	Latin per os (by mouth)
PP	per protocol
PPV	positive pressure ventilation
PR interval	an ECG parameter
QRS interval	an ECG parameter
qRT-PCR	quantitative reverse transcriptase polymerase chain reaction
QT interval	an ECG parameter
QTc	an ECG parameter; values for QT corrected for heart rate
QTcF	QTc corrected according to Fridericia
RBC	red blood cell
RSV	respiratory syncytial virus
SAE	serious adverse event
SAP	statistical analysis plan
SBP	systolic blood pressure
SOC	standard of care
SSRE	sample size re-estimation
Study drug	VIS410 or placebo
SUSAR	suspected unexpected serious adverse reaction
TCID ₅₀	half-maximal tissue culture infective dose
TEAE	treatment-emergent adverse event
VAS	visual analog scale
VIS410	investigational product
WHO	World Health Organization

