8.1 Prior & Concomitant Therapy

All medications taken within 7 days prior to signing of the informed consent form will be documented in the EDC. All therapies other than the study drug administered from signing the informed consent form until the last study visit must be recorded in the EDC system (name of the drug, dosage, route, and dates of administration).

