## 2 STUDY DESIGN AND OBJECTIVES

### 2.1 Trial Design

This is a Phase 2b, multicenter, randomized, double-blind, controlled study comparing the efficacy and safety of 2 dose levels of VIS410 (2000 and 4000 mg) in combination with oseltamivir vs oseltamivir alone in hospitalized subjects with influenza A infection requiring oxygen support. Subjects will be randomly assigned at a ratio of 1:1:1 using a permuted block randomization method to receive VIS410 at a dose of 2000 mg (low dose) or 4000 mg (high dose) or placebo (0.9% sodium chloride), administered as a single IV infusion over 2 hours. Randomization will be stratified by presence or absence of positive pressure ventilation (PPV) at baseline to ensure an even distribution across treatment arms. All subjects will receive oseltamivir 75 mg twice daily (BID) for 5 days (total of 10 doses) as part of standard of care. Treatment with oseltamivir may be extended for up to 5 additional days (up to 20 doses of total therapy) if clinical symptoms warrant further treatment as assessed by the Investigator. Depending on standard of care, subjects may have started oseltamivir therapy prior to randomization. All subjects will also receive a pretreatment regimen of diphenhydramine 50 mg PO or IV plus either ibuprofen 400 mg PO or acetylsalicylic acid 320-325 mg PO approximately 60 minutes before infusion. Approximately 120 evaluable subjects (40/arm) with confirmed influenza A infection will be treated.

Study assessments are outlined in the Schedule of Assessments (copy in Appendix 16.2). Subjects discharged from the hospital prior to Day 14 will attend the applicable out subject follow-up visit(s) (e.g., Day 3, Day 5, Day 7, Day 14) per Table 1. The total study duration for each subject (screening through study exit) will be approximately 8 weeks (Day 56).

January 17, 2019

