-  If the subject has any history of delayed gastric emptying, including premenstruation syndrome or menstruation, he or she may receive oral premedications 120 minutes prior to IV VIS410/placebo infusion.
-  VIS410/placebo will be administered over 2 hours. Infusion time can be extended to up to 4 hours at discretion of the Investigator only if local infusion site-related symptoms occur.
-  Minimum of 10 doses of oseltamivir treatment (BID for 5 days) is required. Treatment with oseltamivir may be extended for up to 5 additional days (up to 20 doses of total therapy) if clinical symptoms warrant further treatment as assessed by the Investigator. Note: based on SOC, subjects may have started oseltamivir therapy prior to randomization. For patients unable to swallow, oseltamivir capsules can be opened and mixed with liquid for ease of administration.
-  To be obtained up to 2 hours post-VIS410 administration.
-  Nasopharyngeal swabs will be obtained for virology and/or PK from both nostrils (1 swab per nostril). The first 50 randomized subjects will have nasopharyngeal swabs collected up to Day 56 (predose, end of infusion, Days 3, 5, 7, 14, 28 and 56); while in the remaining subjects, nasopharyngeal swabs will be obtained up to Day 14 only.
-  If the subject remains in the hospital on Day 10, additional nasopharyngeal swabs will be obtained on Day 10.
-  One tracheal aspirate sample for virology and PK will be obtained (ventilated subjects only).

January 17, 2019

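### As worded, SAP 7 leaves drugs first started on days after the infusion outside both the prior and the concomitant medication definitions

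*SAP*

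**What the plan says.** SAP 6.3 states: "Prior medications are defined as medications that start before the study drug IV infusion". SAP 7 defines concomitant medications as "medications that are being taken while on study drug" and adds two rules for overlap. A prior medication that cannot be shown to have stopped before the infusion is both prior and concomitant, and so is a medication ongoing on the infusion date. SAP 7 and SAP 4.2 provide three classes for the listings: prior, concomitant, and both.

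The protocol's list of abbreviations defines study drug as "VIS410 or placebo". SAP 2.1 says that it is "administered as a single IV infusion over 2 hours", and a footnote to the schedule in SAP 16.2 sets the upper limit: "Infusion time can be extended to up to 4 hours at discretion of the Investigator only if local infusion site-related symptoms occur".

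On collection, Protocol 8.1 says: "All therapies other than the study drug administered from signing the informed consent form until the last study visit must be recorded". Protocol 7.6 documents medications up to the last follow-up evaluation. The concomitant therapy row of the schedule, in Protocol Table 1 and in SAP 16.2, is marked at baseline and at Day 56.

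**The concern.** The SAP ties the concomitant window to time on study drug. That wording suits a course of repeated dosing. Here exposure is a single infusion, so the window closes within hours while medication recording runs for about eight weeks.

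The drugs at risk are those that help a reader interpret safety by arm: treatments begun for adverse events after the infusion, antibiotics begun during follow-up, and antivirals that Protocol 8.2.2 does not permit after randomization. Protocol 4.3 names use of concomitant medications as part of the DSMB's assessment of safety. Protocol 11.4 defines the intervention that counts toward a dosing pause by IV fluid and an antidiarrheal drug. Adverse event tables that run through follow-up would sit beside a medication table that, read literally, omits drugs started on later days to treat those events.

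**Working it through.** No figure in the plan needs reproducing. The check applies the SAP's definitions to each possible timing of a medication relative to the infusion.

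**Inputs.** Prior: SAP 6.3. Concomitant and overlap rules: SAP 7. Date imputation: SAP 4.2. Meaning of study drug: the protocol's abbreviations. Infusion length of 2 to 4 hours: SAP 2.1 and 16.2. Collection to the last visit: Protocol 7.6 and 8.1, and the schedule in both documents.

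**Classification by timing.**

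1. Started and stopped before the infusion: prior.
2. Started before the infusion and continuing, or stop not confirmed: both.
3. Started during the infusion: concomitant.
4. Started later on the infusion date, after the infusion ended: outside the main definition. The rule for drugs ongoing on the infusion date might catch it, but that rule would label it prior as well, although it did not start before the infusion.
5. Partial start date that matches the infusion month and year, or only the infusion year with the month missing: SAP 4.2 imputes the infusion date, so it is handled as a start on that date (item 3 or 4).
6. Started on any later day: not prior, because it did not start before the infusion. Not concomitant, because the subject is no longer on study drug. Neither overlap rule reaches it.

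Item 6 is the gap. Read literally, such a drug appears in neither the prior medication tables (14.1.5.1 and 14.1.5.2) nor the concomitant medication table (14.1.6.1), and no listing class fits it.

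**Does a wider reading of study drug close the gap?** No. If oseltamivir were counted, its planned course is 5 days with up to 5 more, so 5 + 5 = 10 days at most. Drugs started between then and Day 56 would still be unclassified. The protocol's definition does not include oseltamivir in any case.

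**Comparison within the SAP.** SAP 12.1 defines a treatment-emergent adverse event by a start on or after the infusion date, with no end tied to exposure. SAP 7 has no matching clause.

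**The case against.** The strongest reply is that the intended meaning is clear. The schedule marks concomitant therapy through Day 56. Protocol 7.6 applies the term to medications recorded throughout the study, and Protocol 8.2.2 uses it for drugs given after randomization. SAP 4.2 has imputation rules for concomitant medication dates that can apply to months after treatment. The three classes cover every record only if concomitant runs from the infusion onward. A sensible programmer would probably code it that way.

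This stands as evidence of intent, and it means that omission from the table is not certain. It does not amend the definition. SAP 4.1 requires analyses to follow the SAP and deviations to be documented in the study report. A programmer who follows the text omits these drugs, and one who corrects it departs from the plan.

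The second reply, that the consequences are small, also stands. SAP 7 lists all medication data. Antibiotic use for bacterial pneumonia (SAP 9.2.7) and days of oseltamivir (SAP 9.2.5) are summarised separately. No test, endpoint or analysis population uses Table 14.1.6.1.

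A reader might infer that efficacy results are affected, because SAP 9.2.7 names concomitant medications as a source for bacterial pneumonia and SAP 9.2.3 refers to antipyretic and vasopressor use. The documents do not support this. SAP 9.2.7 sets its own timing, including antibiotics begun on Day 1 or later and lasting more than 2 days. SAP 9.2.3 does not refer to the SAP 7 classes. Both can be run on the recorded data.

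**Conclusion.** The definition in SAP 7 is wrong as worded and should be corrected. It conflicts with the protocol's collection period and with the SAP's own adverse event window. The conclusion assumes that study drug has the protocol's meaning and that the rule is applied literally.

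The effect is limited to one descriptive safety table and the classification flag in the listings. The finding does not extend to every drug begun after the infusion, since some same-day starts and some partial dates may be captured. A reader might also be tempted to size the problem by comparing the infusion's few hours with the 56-day follow-up. That ratio measures clock time, not medications or subjects, and the documents give no figure from which the number of omitted drugs could be estimated.

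**What to change.** Replace the definition in SAP 7 with: any medication taken on or after the start of the IV infusion through the last study visit, whether begun before or after that start. Keep the class of both for medications begun before the infusion and continuing into it. The three listing classes then cover every record, and Table 14.1.6.1 covers the same follow-up as the adverse event tables. The cost is one SAP sentence. No new data are needed.
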